2.2.1.1.3 META-ANALYSIS OF ADULT AND PEDIATRIC SAFETY

A meta-analysis of AE data is shown for adults and children using forest plots of total solicited AEs in vaccinees and placebos in the randomized, double-blind, placebo-controlled trials analyzed to date (**Figure 2**). In all cases, 95% confidence intervals cross a ratio of 1, indicating no differences between vaccinees and controls.

Figure 2. Effect of Vaccine on Incidence of any Solicited Systemic Adverse Event (AE) per Study Participant in Randomized, Double-Blind, Placebo-Controlled Trials of PfSPZ Vaccine in Adults Age ≥ 18 Years in Sub-Saharan Africa

[figure not shown]

#Vac. is the number of participants enrolled in the vaccine arm in each study; # Plac. is the number of participants enrolled in the NS control arm of each study.

Numbers in parentheses are the number of participants experiencing any solicited adverse event (AE) after any of the injections administered. Solicited local AEs were collected for three days (BSPZV2, BSPZV3, EGSPZV2 and EGSPZV3) or seven days (BSPZV1, EGSPZV1, BFSPZV1 (DMID protocol ID 15-0001), MLSPZV1 and MLSPZV2 (DMID protocol ID 16-I-N004)) after each dose, while solicited systemic AEs were collected for seven days after each dose, except for MLSPZV1, for which they were collected for 28 days after each dose. Depending on the trial, solicited local AEs included pain, tenderness, erythema, swelling, induration and pruritus; solicited systemic AEs included fever (measured), fever (subjective), headache, fatigue/malaise, arthralgia, myalgia, rash/pruritus/urticaria, chills/rigors, nausea/vomiting, abdominal pain, diarrhea, chest pain, palpitations, shortness of breath, bradycardia/tachycardia, hypertension/hypotension.

Figure 3. Effect of vaccine on incidence of any solicited systemic adverse events per study participant in randomized, double-blind, placebo-controlled trials of PfSPZ Vaccine in infants and children aged 5 months to <18 years in sub-Saharan Africa.

Trial sites included: Bagamoyo, Tanzania (BSPZV2); Siaya, Kenya (KSPZV1b); and Bioko Island, Equatorial Guinea (EGSPZV2). #Vac. is the number of participants enrolled in the vaccine arm in each study; # Plac. is the number of participants enrolled in the NS control arm of each study. Numbers in parentheses are the number of participants experiencing the AE after any of the injections administered. V = vaccine recipients, NS = normal saline recipients, OR = odds ratio, LCL = lower confidence limit, UCL = upper confidence limit. Weight is based on sample size and is represented by the width of the blue bar.

2.2.1.1.4 HUMAN SERUM ALBUMEN

PfSPZ Vaccine is formulated with human serum albumin. The manufacturer CSL Behring states in the package insert: "AlbuRx® 5, Albumin (Human) 5% solution is made from human plasma. Products made from human plasma may contain infectious agents, such as viruses, that can cause disease. The risk that such products will transmit an infectious agent has been extremely reduced by screening plasma donors for prior exposure to certain viruses, by testing for the presence of certain current virus infections, and by inactivating and/ or removing certain viruses through alcohol fractionation and through heat treatment of the product in the final container for 10 hours at 60°C. Despite these measures, such products can still potentially transmit disease. A theoretical risk for transmission of Creutzfeldt-Jakob Disease (CJD) is considered extremely remote. No cases of transmission of viral diseases or CJD have ever been identified for Albumin (Human). There is also the possibility that unknown infectious agents may be present in such products."

in the KSPZV1 trial in Kenya (#12 in **Table 4**). Although many infants experience febrile seizures in association with malaria or other infections in that trial, these febrile seizures were expected adverse events not linked to immunization. It was noted that epilepsy was diagnosed in several children during the KSPZV1 trial, at a frequency not statistically different from the known background rate of epilepsy in the same population. Until larger numbers of children have received PfSPZ Vaccine, Sanaria recommends excluding any individuals with a history of non-febrile seizures from participation in clinical trials of PfSPZ-based products, although with further clinical experience this restriction may be lifted. This exclusion applies to the USSPZV7 trial.

Although the data indicate that PfSPZ Vaccine does not cause adverse reactions at the doses planned for this study, nevertheless the consent form lists the following reactions any vaccine might theoretically cause, including: objective fever (oral temperature $> 100.4^{\circ}$ F), subjective fever, chills, headache, fatigue, malaise, myalgia, arthralgia, rigors, and systemic reactions that might indicate allergic responses (rash, urticaria, pruritus, and edema); these will constitute the list of solicited adverse events which are assessed after each immunization. Additional risks are abnormal laboratory tests, including elevated liver function tests and transient changes in blood counts. Because the vaccine is administered by DVI into a superficial vein, the participant is also at risk of having a vasovagal response.

2.2.1.2 RISK ASSOCIATED WITH PFSPZ CHALLENGE

2.2.1.2.1 LOCAL REACTIONS

As with PfSPZ Vaccine, DVI is used for administration of PfSPZ Challenge. Potential risks include: pain, tenderness, erythema, bruising, swelling and induration. Other potential risks, which have not been observed, but are theoretically possible include local inflammatory reactions, pruritus, large local reactions involving the whole forearm, lymphangitis and lymphadenopathy. Additional risks associated with venipuncture are listed below.

2.2.1.2.2 SYSTEMIC REACTIONS

Like the administration of PfSPZ Vaccine, administration of PfSPZ Challenge has been very well tolerated. Prior to the potential onset of malaria (6 or more days post administration of PfSPZ Challenge), potential risks include systemic allergic reactions to the sporozoites or the diluent (including anaphylaxis), and other reactions typical of vaccines, including objective fever (oral temperature $> 100.4^{\circ}$ F), subjective fever, chills, sweats, malaise, fatigue, headache, myalgia, arthralgia, rigors, chest pain, abdominal pain/tenderness, nausea, vomiting and diarrhea. Additional risks are abnormal laboratory tests, including elevated liver function tests and transient changes in blood counts. Because it is administered via DVI, there is also the risk of a vasovagal response. The incidence of any of these potential risks has been comparable to the risks after the administration of NS in randomized, double-blinded, placebo-controlled trials.

PfSPZ Challenge is formulated with human serum albumin like PfSPZ Vaccine, and carries the same theoretical risks associated with HSA as mentioned for PfSPZ Vaccine.

2.2.1.3 RISK ASSOCIATED WITH *P. FALCIPARUM* PARASITEMIA

Participants undergoing CHMI may be expected to develop malaria, and may experience signs and symptoms of malaria which include subjective fever, objective fever ($>100.4^{\circ}\text{F}$), chills, rigors, headache, vomiting, nausea, dizziness, malaise, insomnia, diarrhea, fatigue, sweats, myalgia, neck ache, arthralgia, abdominal pain, tachycardia, abnormal laboratory tests, (e.g. decreased leukocytes, platelets, mild anemia) and, rarely, enlarged liver or spleen. In study participants from the US and Europe, parasitemia presents between days 7 and 17 in both vaccinees and normal saline controls. No parasitemias have been detected beyond 17 days; study participants who remain negative by qRT-PCR on day 28 do not progress to patent parasitemia and have been safely managed without terminal antimalarials in the most recent CHMI studies (NCT02601716, NCT02704533, NCT04966871). The clinical outcomes of participants post-CHMI are discussed in detail in the published literature [58].

Complications can occur during malaria when diagnosis and treatment are delayed and high parasite densities develop in the blood. In uncontrolled circumstances, malaria infections can lead to kidney, liver, or brain injury (seizures, coma) and death. Under the carefully controlled conditions and implementation of early diagnosis and antimalarial treatment in this study, the chance of such complications is low and the risk of death from malaria infection is very small. There have been no cases with complications resulting in severe disability or death in study participants undergoing CHMI. Participants are monitored closely and treatment is initiated immediately upon identification of parasitemia.

Cardiac events have been reported following CHMI in clinical trials in the Netherlands at Radboud University Nijmegen Medical Center (RUNMC). In all cases these events followed CHMI from the bites of infected *Anopheles* sp. mosquitoes. Similar events have not been seen following the administration of PfSPZ Challenge at this or other clinical trial sites.

It remains unclear whether any of these events are related to Pf parasites or the treatment of Pf parasitemia. While there are confounding factors associated with each of these cardiac events, including the peculiar fact that these events have occurred only at one center following CHMI by the bite of infected *Anopheles* sp. mosquitoes, and never following PfSPZ Challenge inoculations by DVI or PfSPZ inoculations by mosquito bite performed elsewhere, nevertheless a causal relationship with CHMI cannot be excluded and therefore the design of the USSPZV7 trial will incorporate safeguards to minimize to the extent possible the risk of cardiovascular events in study participants. Enrolled participants will be at low risk of cardiovascular events due to their age, absence of known cardiovascular disease, absence of known diabetes mellitus, and documented normal EKG, systolic and diastolic blood pressure at screening. During the study, participants will be closely followed for the occurrence of cardiovascular-related signs or symptoms. Monitoring will include questioning about chest pain, palpitations and shortness of breath starting on day 7 after administration of PfSPZ Challenge (7G8). Signs or symptoms of an event suggestive of a cardiac etiology will prompt a cardiology work-up.

Relapsing malaria is not an issue since Pf has no hypnozoite stage and therefore does not relapse after appropriate treatment.

2.2.1.4 RISK ASSOCIATED WITH VENIPUNCTURE

At specified points throughout the study, blood samples will be collected from the participant for safety laboratories and qPCR. There are risks associated with blood drawing that include discomfort, swelling, bruising around the vein, lightheadedness/fainting, anemia following repeated blood draws, and, rarely, infection at the blood-drawing site or clinically significant hematoma. Infection could lead to more generalized symptoms such as limitation of arm movement, lymphadenopathy, fever, chills, headache, malaise, myalgia, joint pain or sepsis.

2.2.1.5 RISK ASSOCIATED WITH ANTI-MALARIAL MEDICATIONS

Malarone® (atovaquone/proguanil), a generally well tolerated and highly effective treatment regimen, will be used as the first line anti-malarial treatment for all participants. Second-line treatment will be Coartem® (artemether/lumefantrine). The study team will discuss these medications and their possible side effects in detail as part of the informed consent process and prior to initiation of treatment for participants who are infected with malaria.

Side effects of atovaquone/proguanil (Malarone®) include: nausea, vomiting, abdominal pain, anorexia, diarrhea, headache, cough and, rarely, anemia, oral ulcerations, insomnia, fever, edema, and alopecia.

Side effects of artemether-lumefantrine (Coartem®) for those participants who cannot tolerate Malarone® include:

Common side effects: abdominal pain, nausea, vomiting, anorexia, chills, cough, heart palpitations, fever, headache, myalgia, sore throat, nasal congestion, dyspnea on exertion, dizziness/vertigo, insomnia, hepato- or splenomegaly, elevated AST, pruritus/rash, easy bruising, fatigue and weakness.

Serious side effects: bleeding significant enough to cause melena and hematuria, dysuria, changes in hearing, chest pain, seizures, hypersensitivity reaction, QT prolongation and bullous dermatitis.

2.2.1.6 PREGNANCY

Risks to unborn babies are unknown at this time; pregnant females will be excluded from this study. Study participants should not become pregnant for 2 months after CHMI. Sexually active females, unless surgically sterile or post-menopausal, must use an effective method to avoid pregnancy (including oral or implanted contraceptives, intrauterine device, female condom, diaphragm with spermicide, cervical cap, abstinence, use of a condom by the sexual partner or surgical sterilization of sexual partner). If post-menopausal, female participants must have experienced at least 1 year of amenorrhea.

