4.7 END OF STUDY DEFINITION

End of Study: A participant is considered to have completed the study if he or she has completed all phases of the study including the last visit and all scheduled procedures as shown in Section 1.3 ‘Schedule of Activities’.

Early termination: A participant will be considered an early termination if he or she withdraws from the study or is withdrawn from the study by the site PI, or is lost to follow- up, prior to the last visit and a study termination form has been completed.

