5. STUDY POPULATION

5.1 INCLUSION CRITERIA

To be eligible to participate in this study, an individual must meet all of the following criteria:

- Healthy adults (male or non-pregnant female) 18 to 50 years of age.
- Able and willing to participate for the duration of the study.
- Able and willing to provide written informed consent and satisfactorily complete a test of understanding with a passing score $\geq 80\%$.
- Physical examination and laboratory results without clinically significant findings.
- Women of childbearing potential must agree to use effective means of birth control (e.g. oral or implanted contraceptives, IUD, female condom, diaphragm with spermicide, cervical cap, abstinence, use of a condom by the sexual partner or sterile sexual partner) during the entire study. Women with a history of surgical or chemical sterilization (e.g. tubal ligation, hysterectomy, other).
- Willing to refrain from blood donation for 3 years following CHMI.
- Agree not to travel to a malaria endemic region during the trial.

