5.2 EXCLUSION CRITERIA

An individual who meets any of the following criteria will be excluded from participation in this study:

- Unable to provide informed consent including inability to pass the test of understanding, which is written in English for the US-based study sites.
- Receipt of a malaria vaccine in a prior clinical trial.
- History of a splenectomy or sickle cell disease.
- History of a neurologic disorder (including non-febrile seizures or complex febrile seizures) or formal history of migraine headache.
- Current use of systemic immunosuppressant pharmacotherapy.
- Receipt of a live vaccine within 4 weeks of first immunization or of 3 or more non-live vaccines within 2 weeks of first immunization.
- Women who are breast-feeding, pregnant or planning to become pregnant during the study period.
- Known allergy to atovaquone-proguanil (Malarone®), artemether-lumefantrine (Coartem®), or any component of the investigational products.
- A history of malaria in the 2 years prior to screening.
- Participation in any study involving investigational vaccine or drug within 4 weeks prior to enrollment that in the estimation of the site PI might adversely affect the individual’s safety or

the quality of data to be collected.

- Evidence of increased cardiovascular disease risk; defined as >10% five-year risk by non-laboratory method (Gaziano, 2008) [69].
- Plan to participate in another investigational vaccine/drug research during the study.
- Plan for major surgery between enrollment until 28 days post-CHMI.
- Use or planned use of any drug with anti-malarial activity that would precede or coincide with malaria challenge or vaccination.
- Anticipated use of medications known to cause drug reactions with atovaquone-proguanil or artemether-lumefantrine such as cimetidine, metoclopramide, antacids, and kaolin.
- Positive HBsAg or positive HIV or HCV testing consistent with active infection.
- An abnormal electrocardiogram, defined as one showing pathologic Q waves and significant ST-T wave changes; left ventricular hypertrophy; any non-sinus rhythm including isolated premature ventricular contractions, but excluding isolated premature atrial contractions; right or left bundle branch block; or advanced (secondary or tertiary) A-V heart block; or other clinically significant abnormalities on the electrocardiogram as determined by the consulting cardiologist.

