8.1.6.5 FINAL VISIT: +56 DAYS POST-CHMI

Participants will have medical history and concomitant medication update, vital signs taken and directed physical exam performed (if indicated). Any AEs or SAEs that are unresolved at that time will be continued to be followed until resolution or stabilization, or, if a serious or chronic condition has developed, until it has stabilized.

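### The contraception commitment and pregnancy-plan exclusion run only to the end of the study, which can fall before the 2-month post-CHMI period in Section 2.2.1.6 has passed

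*Combined protocol and SAP*

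**What the plan says.** Section 2.2.1.6 (Pregnancy) describes the risk to a fetus as unknown and gives a period of avoidance: "Study participants should not become pregnant for 2 months after CHMI". The next sentence adds a duty without an end date: "Sexually active females, unless surgically sterile or post-menopausal, must use an effective method to avoid pregnancy".

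The eligibility criteria set their own durations. Section 5.1 says "Women of childbearing potential must agree to use effective means of birth control", and the duration attached to that agreement is "during the entire study". Section 5.2 excludes "Women who are breast-feeding, pregnant or planning to become pregnant during the study period". Neither criterion mentions a period after CHMI, and nothing elsewhere in the text available links them to the one in Section 2.2.1.6.

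Section 4.7 defines when a participant's study ends: "A participant is considered to have completed the study if he or she has completed all phases of the study including the last visit". Section 8.1.6.5 is headed "FINAL VISIT: +56 DAYS POST-CHMI". The synopsis gives follow-up for each participant as 8 weeks after CHMI. In Table 3 (Section 1.3), the last entry of the windows row is plus or minus 10 days in both the 3-week and the 12-week schedule.

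**The concern.** The risk section counts from CHMI, whereas the two criteria count to the end of the study. If the study ends for a woman before 2 months have passed, she can satisfy both criteria and still plan a pregnancy that begins inside the period the protocol tells her to avoid.

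The stake is participant protection. The last scheduled pregnancy test is the one before CHMI (Table 3 and Section 8.2.2.2), so after challenge the protection rests on what the participant agreed to. The trial also aims for at least 50% women, so the wording will be applied often. Nothing in the efficacy endpoint, the sample size or the analysis populations depends on it.

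**Working it through.** **Inputs**

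- Avoidance period: 2 months after CHMI (Section 2.2.1.6). The protocol does not convert this to days. Two readings are carried through: 8 weeks = 56 days, and calendar months = 59 to 62 days depending on the start date.
- CHMI day and final-visit day (Table 3): Days 50 and 106 in the 3-week schedule; Days 113 and 169 in the 12-week schedule.
- Window on the final visit: plus or minus 10 days, the last entry of the windows row in both schedules.
- End of the commitment: the participant's last visit (Sections 5.1, 5.2 and 4.7).

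**Step 1: reproduce the plan's final-visit timing.** 106 − 50 = 56 and 169 − 113 = 56. Both cohorts agree with Section 8.1.6.5.

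**Step 2: apply the window, counted from the actual CHMI day.** Earliest: 56 − 10 = 46. Latest: 56 + 10 = 66.

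**Step 3: shortfall = avoidance period − day of final visit.**

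| Final visit | 2 months as 8 weeks (56 d) | 2 calendar months (59–62 d) |
|---|---|---|
| CHMI+46 (earliest) | 56 − 46 = 10 d | 59 − 46 = 13 to 62 − 46 = 16 d |
| CHMI+56 (nominal) | 56 − 56 = 0 d | 59 − 56 = 3 to 62 − 56 = 6 d |
| CHMI+66 (latest) | none (10 d to spare) | none (66 − 62 = 4 to 66 − 59 = 7 d to spare) |

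On the calendar reading, the commitment covers the whole period only if the final visit falls at about CHMI+59 to CHMI+62 or later. On the 8-week reading, it does so from the nominal visit onward.

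**The case against.** The case against rests on five points, and each limits the finding.

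- **Meaning of 2 months.** Follow-up is described in weeks and the final visit is at 8 weeks, so 2 months may be shorthand for the same thing. If so, there is no gap at the nominal visit. The gap at an early visit remains.
- **Meaning of the study.** The synopsis also speaks of the whole trial, at about 12 months, and gives participant duration separately. If Section 5.1 means the trial, the gap closes, at least for everyone not among the last challenged. Section 4.7 and the per-participant follow-up in the synopsis favour the narrower reading, but the criterion does not say which it intends.
- **The window.** In the copy available, the windows row of the 3-week schedule has 25 entries for 28 visit columns. Assigning the last entry to the last visit is sensible, because it is the same in both schedules, but it is an inference. The nominal-visit result does not need it.
- **The duty in Section 2.2.1.6.** That section already requires an effective method with no end date. The gap therefore lies in the eligibility wording, not in every statement about contraception.
- **Consent text.** The consent pages are not in the copy available and may state a duration. Nothing is inferred from them.

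Three stronger readings are tempting, and the documents do not support them.

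- A reader might infer a shortfall of up to about 2 months for a woman who withdraws soon after challenge. No eligibility wording binds someone who has withdrawn, so this is not a defect of the criterion. Section 7.4 separately provides for treatment and a safety visit at CHMI+28.
- A reader might infer a gap for women vaccinated but never challenged. Section 2.2.1.6 sets no period for them, so nothing is contradicted.
- A reader might take half of the 60 participants as affected. That counts every woman enrolled, including those who are sterilised or post-menopausal and those whose final visit falls late enough to leave no gap.

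**Conclusion.** The inconsistency is real and small. As written, the enrolment commitment can end before the avoidance period that the protocol itself states: by 10 to 16 days at the earliest visit the schedule appears to permit, and by 0 to 6 days at the nominal visit. For a visit late in the window there is no shortfall.

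This rests on three assumptions: that the study in Sections 5.1 and 5.2 means the participant's own participation, that the 10-day window belongs to the final visit, and that the window is counted from the actual CHMI day. The early-visit gap survives both readings of 2 months. The nominal-visit gap exists only on the calendar reading.

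It is a minor participant-protection and consistency point, and it does not bear on power or the efficacy analysis.

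**What to change.** Reconcile Sections 2.2.1.6, 5.1 and 5.2 so that the contraception commitment, the pregnancy-plan exclusion and the stated avoidance period all run to the same point after CHMI, whatever the date of the final visit. State that point in units that leave no doubt between weeks and calendar months. Which period applies is for the sponsor to decide; none is proposed here. Confirm at the same time that the window shown last in Table 3 belongs to the final visit, and check that the consent form agrees with the reconciled text.

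The cost is about one sentence in each criterion and any matching consent wording. No visit, test or analysis is added.
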